C8. Power: We made an estimate for group size using two approaches. We used the statistical map of magnitude from 20 AUD subjects and 20 CS that had been compared with 3dANOVA as input to two power calculators. We used *fmripower* (Mumford and Nichols, 2008), a MATLAB-based program that calculates a power estimate given the between-group and within-subject error terms associated with a two-tailed t-test of regression coefficients. We also used Neuropower, an online toolkit that calculates group sizes from statistical maps. For whole brain analyses, the results from *fmripower* suggested that 31 subjects per group would yield a power of .8 for the test comparison, while Neuropower suggested 29 and 45 subjects per group with the Benjamini-Hochberg and Random Field theory correction for multiple comparisons, respectively. When we used the ROIs in **Table 3** to mask the voxels in the statistical map, power for 50 subjects per group was 0.99. We are, therefore, confident that the proposed 50 subjects per group will provide us with sufficient power to test the predictions.

[figure not shown]
C9. Timeline, Benchmarks:

Timeline for this 4-year project is presented in graphical form (**Figure 4**).

C10. Risk to Subjects

Human Subjects Involvement: Approximately 200 individuals will be recruited for this project.

Potential subjects will call [name] or his designee after seeing a presentation about the study, in response to a study advertisement or by referral from a clinician. All subjects will have been offered a flyer with contact information. When subjects call, they will undergo a brief telephone interview to determine if they are likely to

qualify and, if so, will be invited for visit 1. Subjects may also be screened at treatment centers during recruitment visits. Each subject will then give informed consent before any data collection takes place. Study visits may take place at the Portland VA, OHSU or at local treatment centers.

Sources of Materials: All study data derived from subject procedures (including behavioral working memory and discounting tasks, neuropsychological tests, screening interview questionnaires and MRI scan) is obtained specifically for research purposes and not for treatment. Blood specimens will be obtained and analyzed by the VA lab and destroyed according to protocol or banked for future research. Blood samples may also be drawn by study team doctors or by study staff who have undergone OHSU's phlebotomy draw class. UA will be obtained and analyzed by the research team or the VA lab and will be destroyed according to protocol. MRI scans are obtained at the Advanced Imaging Research Center at OHSU and the data are downloaded to a computer located at the VA.

Potential Risks: This study does not involve treatment or invasive procedures. Participants may become upset while answering personal questions during the interview or during administration of the neuropsychological tests.

Subjects who are claustrophobic may become frightened in the MRI machine. Subjects with metal fragments, wire sutures, staples, implanted pacemakers or defibrillators or metal fragments from welding are at [name]

risk from damage due to movement of metal fragments in the 3T magnetic field. Participants will be systematically assessed for ferromagnetic metallic foreign bodies and excluded if there is any doubt. Rarely, subjects experience vertigo, a metallic taste or muscle stimulation. Although none are currently known, there may be unknown risks to fetuses from the MRI procedure.

Subjects may experience an increase in cue-induced craving if they are in recovery from a substance use disorder as a result of their assessment, particularly on the craving task, the DSNBACK.

As there are risks to confidentiality, particularly if sensitive information about drug use and abuse and past legal problems were sought. We will apply for a Certificate of Confidentiality from the NIH for this study.

Blood drawing may cause pain or bruising at the site and carries a small risk of infection.

Adequacy of Protection from Risk

Recruitment and Informed Consent: Members of the research staff will meet regularly with personnel in the VA Substance Abuse Treatment Program (SATP), with inpatient and outpatient psychiatry staff and with the staff at community treatment programs (to enhance recruitment of women and under-represented subject groups), who may refer possible subjects. In addition to referrals from clinicians or responses to advertisements, we will also recruit patients via informational presentations in treatment settings. A study member will give regular presentations of the study at SATP access meetings and at weekly meetings in community treatment centers and detox programs. Attendance at these recruitment meetings by potential subjects is entirely voluntary. Potential subjects will be given the IRB-approved advertisement with contact information and asked to call the contact number if they are interested in participation or screened on site. Any study data or information collected outside of the Portland VA will be kept inside a storage clipboard or on an OHSU-encrypted laptop until it is returned to the VA. Any specimens collected outside of the Portland VA will be kept in a small Styrofoam cooler until they are returned to the VA.

Protection Against Risk: Subjects are interviewed extensively to screen for any contraindication to MRI, e.g., surgical aneurysm clips, pacemaker, prosthetic heart valve, neuro-stimulator, implanted pumps, cochlear implants, metal rods, plates or screws, previous surgery, hearing aids, history of welding, metal shrapnel. If there is any doubt, the subject will be excluded. The research team will obtain orbital x-rays if subjects have any history of welding, grinding or other exposure to metallic particles that could lodge in the orbit. Pregnant women (negative urine pregnancy test required before the scan), because of the unknown risk to the fetus, will also be excluded. Participants will be taken to a mock MRI prior to the procedure if they are concerned about claustrophobia. If a subject becomes frightened during the procedure, it can be terminated immediately.

A clinician will be available to consult with any participants who experience discomfort for any reason during the study visit. Subjects will be asked to remain in laboratory either until the problem has been resolved or immediate referral to appropriate treatment is accomplished. Subjects not in need of emergent treatment will be offered referral to counseling or other support resources as appropriate. Substance-dependent subjects (except control smokers) will all be in remission and undergoing residential treatment to ensure availability of counseling and support after study visits. The subject may request termination of the assessment at any time.

Subjects may refuse any single non-critical procedure in the study if it makes them uncomfortable without disqualification from the rest of the study.

C11. Participation of Non-Veterans: This is an ambitious study and requires recruitment of subjects who have been abstinent less than one month and one group of subjects who have AUD, but do not use nicotine. There are also significant gender effects which necessitate having a gender balanced sample. We will, therefore, need to recruit non-veterans to meet our ambitious recruitment goals, recruit sufficient women and subjects rare in the veteran treatment population. The [name] lab has established relationships with treatment programs within and outside the VA Portland HCS which will facilitate recruitment. Non-veterans will be recruited from community alcohol detox and treatment programs, through advertisement on OHSU's Study Participation Opportunities web page, and, if necessary for controls, Craig's List.

C12. Potential Benefits of Research to Subjects and Others

This project is not intended to benefit individual subjects but results may help us understand the neurobiology of alcohol and tobacco co-addiction and tailor treatment approaches to co-addicted individuals seeking treatment in the future.

C13. Importance of Knowledge to be Gained

The results of this project will be valuable for planning treatment options for dually addicted individuals by [name]

predicting and evaluating treatment response using neuroimaging. A predictive model will help individualize relapse risk through a better understanding of neurobiological factors that influence addiction, craving and cognition.

C14. Data and Safety Monitoring Plans

Data Security and Privacy: Data will be stored in a manner intended to preserve patient confidentiality. Hard-copy PHI will be stored in locked cabinets in the PIs VA office and laboratory space. Electronic PHI will be stored only on servers behind the VA firewall accessed by password-protected VA computers. Each subject is given a unique identifier (UI) based on a random number and study identifier, in this instance NAUDxxx. Only coded or de-identified data, not PHI, are used for analysis. The file linking the UI to the patient's name will be stored in a separate password-protected file on a secure server behind the VA firewall. Once the study has ended, the link will be stored by the VA R&D office (or destroyed if regulations change). The primary repository for coded data and neuroimages will be stored on a password-protected network drive at the OHSU Advanced Computing Center, to which only the research team has access. Coded data will also be stored on OHSU's REDCap application, a highly secure and robust web-based research data collection and management system. No identifiable information will be entered into this application at any time. The statisticians will not have access to the code or PHI at any time. The spreadsheet linking the code to the subject will remain behind the VA firewall at VAPORHCS. Any email contact with subjects will occur through Azure secure email (with the exception of recruitment emails sent to OHSU patients which will use OHSU email).

MRI images are collected at the Advanced Imaging Research Center (AIRC) at OHSU. No PHI is used to identify subjects and only the subject's coded ID is entered at the time of the scan. Images are archived on a separate partition on the AIRC PACS server (AETitle = HOFFNAUD) to which only [name] Lab research computers and the AIRC IT specialist have access. The raw data for each MRI scan is downloaded to [name] Lab Linux workstations in room 5C-107 at the VA. These workstations are, by necessity, hooked up to the OHSU network, but can be accessed only by [name] Lab personnel. Image analysis takes place on these workstations in VA space.

At the end of the study, the AIRC will scrub the partition containing archives and remove the partition, so that the data are permanently erased from the AIRC. The [name] Lab will archive the raw image files in the already established [name] Data Repository (estimated to be about 12 Tbyte).

C15. Blood and Data Banking

Serum, leukocytes (from whole blood samples) and a buccal swab will be obtained (via separate permission on the HIPAA and ICF), linked to study data for coded storage in the MARC Translational Service Core Biorepository ([name], Administrator). No PHI will be stored in the data repository and repository data will be coded by an identifier (NAUDXXX), where XXX is a pseudorandom number. The code for the repository identifier will be identical to the study identifier and there will be a single spreadsheet linking to identifiable information that will be destroyed or encrypted at the closure of this study. Information collected for the contact repository will be stored on a password protected spreadsheet separate from the coded study data and will just have PHI and contact information.

C16. Oversight

IRB-approved study staff will ensure that any protocol deviations or adverse event will be reported immediately to the PI, who will examine the patient and determine if any additional evaluation or treatment is needed. The PI will ensure that significant adverse events are properly reported to the IRB (within 5 days to comply with VA policy). The [name] Lab will examine all cumulative adverse events semi-annually to determine if there are any systematic problems.

C17. Inclusion/Vulnerable Populations

Women and Minorities: Given that gender effects may be prominent in this population, it is important that the ratio of male/female subjects approach 50/50. We will recruit outside of the VA SATP to ensure that women are represented equally with men, in alcohol detox and treatment centers in the Portland area. Minority subjects will be recruited to be a representative cross section of the Portland, Oregon population. That population is primarily Caucasian 82.4%, with 7% African-American, 7%, Asian, 1.8% Native Hawaiian or Other Pacific Islander, and 1.8% Native American. Additionally, the population will be primarily non-Hispanic 93%, with 7% Hispanic. Pregnant Women are excluded and must have a negative pregnancy test.

Children: Children will be excluded from this study.

Prisoners: No prisoners will be included. If subjects are incarcerated at the time of follow-up, they will be dropped from the study.

Decisionally Impaired: Decisionally impaired subjects will not be recruited or included in the study.

C18. Determining VA from Non-VA Research

This study will take place both at the Portland VA and at OHSU. VA Research will include consent, screening, questionnaires, blood draws, urinalyses, and x-rays. Non-VA Research will be only the MRI scans acquired at OHSU's AIRC. Recruitment talks will be given at SATP (VA) and community treatment programs. Screening and study visits may take place at treatment centers.

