C. Research Design and Methods (Figure 1): The overarching aim of this proposal is to neurobiologically characterize and predict the effect of NAUD co-addiction on the outcome of patients who enroll in alcohol abuse treatment. In order to accomplish this goal, we will recruit four subject groups who will be characterized primarily with anatomical and functional neuroimaging (**SA1**). These measures will yield elements that become part of a quantitative predictive model that characterizes the neurobiological signatures of AUD, NUD, CS and NAUD co-addiction (**SA2**). These subjects will be well characterized with respect to their substance use and will then be evaluated with two functional MRI (fMRI) tasks, resting state MRI (rsMRI), high resolution anatomical MRI, standard DWI and high angular resolution diffusion imaging (HARDI). Imaging data will be used to test specific hypotheses about the effects of alcohol and nicotine on the brain and behavior.

C1. Subject Recruitment and Initial Evaluation:

Two hundred subjects, ages 18 to 55, will be recruited from the Portland VA, Oregon Health & Science University (OHSU), community substance abuse treatment

Group	Inclusion Criteria
CS	If any history of severe addictions to other substances must be at least 5 years clean. No history of gambling. Less than 20 lifetime cigarettes or equivalent.
NUD	DSM-V criteria for Nicotine Use Disorder Current Smoker, at least 5 cigarettes/day. If any history of severe addictions to other substances must be at least 5 years clean. No history of gambling.
NAUD	DSM-V criteria for Nicotine Use Disorder and Alcohol Use Disorder. At least 8 heavy drinking episodes in the past month. Current Smoker. Alcohol free from 2 to 8 weeks. If any history of severe addictions to other substances must be at least 5 years clean. No history of gambling.
AUD	DSM-V criteria for Alcohol Use Disorder. At least 8 heavy drinking episodes in the past month. Alcohol free from 2 to 8 weeks. Less than 20 lifetime cigarettes or equivalent. If any history of severe addictions to other substances must be at least 5 years clean. No history of gambling.

Table 1: Inclusion criteria emphasize both diagnostic (DSM-V) and severity of use criteria for each group.

Clinical Interview^a
- Demographics
- Medical History
- Psychiatric History
- Substance Use History – Timeline Followback
 Tobacco Use (Current and lifetime)
 Alcohol Use (Current and lifetimes)

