Currently enrolled subjects or subjects who have completed their participation will have the opportunity to refer others to the study. The referrer will receive a gift card as incentive for each individual who attends their first study visit. In order to protect the confidentiality of the referrer/referee we will not confirm or deny either is enrolled in the study. Interactions with the referrer/referee will have a scripted response to protect confidentiality (see separate word document). We will attempt to contact a current address and payment will only be received if we can verify a current address. We will add a tab to our PHI spread that will include: referrer/referee, outcome, referrer's address and whether referrer received a gift card.

In addition, subjects may be recruited from the previous MARC project (mIRB 8702) where an IRB-approved member of that study will contact individuals who consented to be contacted for future studies by phone. The study team member will give a short overview of the study and give the potential participant contact information for our lab to call if they are interested. Recruiters who directly interact with subjects (e.g., at scheduled visits to SATP intake meetings) will identify subjects who meet criteria for this study (**Table 2**) and obtain informed consent.

We will conduct a CPRS search of patients using Data Access Request Tracking (DART) who are between the ages of 18 and 55 and meet the inclusion criteria listed in table 2 of the protocol to identify potential participants. We will further refine the search by using the following exclusion criteria; a history of medical conditions that affect the brain (i.e., Multiple Sclerosis), any medical problems that may prevent them from being able to have an MRI done, taking medications for anti-psychotics/anti-Parkinson's, or have a current substance dependence besides alcohol or methamphetamine. We will then perform a pre-screening medical record review of individuals who meet the search criteria to identify individuals who meet study criteria. The individual will either be contacted by letter or secure email:

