Subjects who call in response to advertisements will be given a brief screening interview to verify age, gender, treatment status, time abstinent, current medications, concurrent medical illnesses and contraindications to MRI. Additional questions will be asked to screen for recent exposure and symptoms of COVID-19. If recent exposure or symptoms are disclosed, and the subject otherwise qualifies, we will wait to schedule them until they have self-isolated for two weeks from time of exposure and/or when their symptoms have completely resolved. Our screening criteria already excludes those who are at increased risk of severe [name]

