illness from COVID-19; however some subjects who *might* be at an increased risk may still qualify to participate during modified operations including smokers and those with well-controlled moderate-to-severe asthma, hypertension, and/or high blood pressure. These subjects will be informed that they may be at higher risk for COVID-19 infection and they may not want to put themselves at risk by participating in research. Contact information will be collected on the screening form for scheduling purposes and, if the potential subject agrees, email will be collected to send an appointment confirmation email (Azure). Subjects are excluded for significant medical problems or drugs known to affect functional MRI. Subjects who fall under the AUD or NAUD group will undergo a breathalyzer test before consent and at the beginning of visits 2, 3, and 7. If a subject has a blood alcohol content (BAC) above 0.08 they will be either excluded from the study or have the study visit rescheduled. The breathalyzer test result before consent will not be collected and is intended to ensure subject is fully capable of consenting. Subjects will be screened for COVID-19 symptoms during confirmation calls prior to study visits and again at the beginning of each in-person visit along with a temperature check. If any symptoms are revealed, the visit will be rescheduled for at least two weeks or until symptoms are resolved. Subjects will be evaluated per the Standardized Human Participant Protocol used by the Translational Service Core of the Methamphetamine Abuse Research Center (MARC) (**Table 1**). To maximize the quantification of alcohol and nicotine use, the instruments have been modified to emphasize both recent (30 days prior to sobriety) and lifetime substance use with the National Institute of Drug Abuse PhenX Toolkit and the Alcohol Use Disorder and Associated Disabilities Interview Schedule 5 (AUDADIS-5). The evaluation includes diagnostic instruments, a battery of cognitive tests, standard measures of impulsivity, PDD, the Stop Signal task, DSNBACK and the Barratt Impulsiveness scale. NAUD and AUD subjects will be required (as an inclusion criterion) to permit contact with two reliable collateral informants, preferably family members with whom they have regular contact. Collaterals will be contacted to obtain their consent to be an informant for the study and contacted if subjects drop out. Subjects will also be asked to give permission to contact clinicians (case managers, physicians) involved in their care. The [name] Lab has established relationships with community treatment programs (including alcohol-specific centers) from prior projects which will facilitate our recruitment. Subjects who are veterans will also be asked for permission to look at their VA medical records for recent blood test results, medication and drug use, as well as treatment/relapse status. This information may be used as study data and blood test results may be used in lieu of repeat testing for the study.

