C2. Laboratory: Urine drug abuse screen (UDS), thyroid-stimulating hormone test, HIV, Hepatitis C Ab screen, complete blood cell count, creatinine, liver enzymes (aspartate aminotransferase, alanine aminotransferase and gamma-glutamyl transferase) will be performed to ensure subjects meet criteria for inclusion in the study. Urinary cotinine tests will help quantify smoking and urine human chorionic gonadotropin (HCG) tests will screen women for pregnancy (pregnant women will be excluded from the study). [name]

HCG tests may not be performed on women who have been surgically sterilized or who are post-menopausal. HCG will be performed at the initial visit and at the MRI scan visits. UDS will be obtained at all visits.

Comments: In addition to alcohol and nicotine, casual use of cannabis is common. We will exclude any subject who meets criteria for current dependence of cannabis (or any other substance), but will not exclude subjects for casual recreational use (or mild lifetime dependence for drugs other than nicotine and alcohol). We may also accept subjects with current methamphetamine use disorder into the study. We will document the amount of cannabis and other recreational drug use for statistical control purposes. We use < 20 lifetime cigarettes (Pomerleau et al., 2004) for inclusion in our AUD and CS groups. If we encounter significant problems with recruitment, then we will change criteria to 100 lifetime cigarettes.

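### C10 relies on remission and residential treatment for support after visits, but the eligibility text contradicts the first and does not secure the second

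*Combined protocol and SAP*

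**What the plan says.** C10 (Protection Against Risk) makes a flat statement about who the substance-dependent subjects are and gives the reason for it: "Substance-dependent subjects (except control smokers) will all be in remission and undergoing residential treatment to ensure availability of counseling and support after study visits". The same section gives every participant access to a clinician at the visit, a request to stay until a problem is resolved or referred, an offer of counseling referral, and the right to stop or to decline a procedure. C10 (Potential Risks) names a rise in cue-induced craving as a risk and singles out the DSNBACK.

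The text that decides who gets in reads as follows.

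- **Table 1.** AUD and NAUD subjects must be "Alcohol free from 2 to 8 weeks". All four rows add: "If any history of severe addictions to other substances must be at least 5 years clean". No row names a treatment setting.
- **C2, Comments.** "We will exclude any subject who meets criteria for current dependence of cannabis (or any other substance"), and shortly after, "We may also accept subjects with current methamphetamine use disorder into the study". C2 also has urine drug screens at all visits.
- **C1, record searches.** The VA search and the OHSU search both list as excluded those who "have a current substance dependence besides alcohol or methamphetamine".
- **C1, phone screen.** Staff are to "verify age, gender, treatment status, time abstinent, current medications, concurrent medical illnesses and contraindications to MRI". For veterans who agree, VA records may be read for blood results, medication and drug use, "as well as treatment/relapse status".

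**The concern.** C10 describes a population and then draws a protection from that description: because these subjects live in a treatment program, someone is there to support them when they leave the study visit. If the eligibility rules admit people who do not fit the description, the protection is overstated for those people.

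The risk is specific. Before the DSNBACK, subjects pick the 6 alcohol and 6 nicotine images they find most salient, and those images are then used in the scanner (C3b). An AUD or NAUD subject may be as little as 2 weeks alcohol free at entry. Craving that starts or lasts after the subject has gone home is what residential support would catch. A reader judging risk from C10 would assume it is caught for everyone concerned.

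**Working it through.** The plan gives no figure on this point and no arithmetic applies. The check is to hold each half of the C10 sentence against the text that controls entry.

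**1. Remission.**

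- For alcohol, the 2-to-8-week alcohol-free rule in Table 1 gives the statement partial support.
- For methamphetamine, C2 and both record searches point the other way. The allowance therefore appears in three places and is not a single slip. On an ordinary reading a current use disorder is not remission, so the word all in C10 cannot stand beside C2.
- The allowance also sits badly with the other eligibility rules. C2 excludes current dependence on any other substance. Table 1 requires 5 years clean where the other addiction was severe.
- One could try to reconcile these by distinguishing a milder use disorder (accepted) from dependence (excluded). The record searches defeat that reading, because they exempt methamphetamine dependence itself.
- Read literally, the sentence also misses on nicotine: NAUD subjects are current smokers by definition and are not the control smokers it exempts. The natural sense is alcohol and other drugs, so I place no weight on this.

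**2. Residential treatment.**

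| Place | What it says about setting |
|---|---|
| C10, Protection Against Risk | residential, for all except control smokers |
| Table 1 | nothing |
| C1, phone screen | treatment status is verified; no setting is required |
| C1, record searches | nothing |
| C2 | nothing |

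Recruitment is not confined to residential programs. C1 allows flyer packets for AA meetings and flyers in retail locations, primary care clinics and emergency departments. C10 (Recruitment and Informed Consent) includes referral through outpatient psychiatry staff. Some of these routes may mainly serve the control and smoking groups. The AA packets, and record searches that leave current alcohol dependence in, are plainly aimed at alcohol subjects as well.

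**3. What depends on the residential condition.** The clinician, the stay until resolution and the offer of referral act at the visit, or depend on a problem being noticed there. Beyond the visit:

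- The two-week calls in C1 are optional, follow Visits 3, 4 and 5, and are there to keep contact and limit drop-out.
- Craving is rated before and after the scan (C3b), but no action follows from a rise.
- Journals record craving (C3b2), but they are handed in at monthly visits.

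Residential care is therefore the only stated means of ensuring support between leaving the visit and the next contact.

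**The case against.** **Table 1 is not the whole list of criteria.** The collateral-informant requirement is an inclusion criterion placed in the text of C1, and the pregnancy exclusion is in C2 and C10. The C10 sentence could itself be the residential requirement, applied through the treatment-status question at the phone screen. C's opening also frames the target as patients enrolling in alcohol treatment, and a recruitment route is not an eligibility rule. This stands in part: silence in Table 1 is weak evidence by itself. What remains is that no screening step is told to apply the condition, and C10 is worded as a description of the sample, not as a test for entry.

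**Current need not mean active.** The record searches let current alcohol dependence through, yet AUD and NAUD subjects must already be abstinent, so in this plan a current diagnosis can go with early abstinence. That is fair for alcohol, where an abstinence window is written down. For methamphetamine there is none. The only abstinence rule that could reach it is 5 years clean, which does not fit a current disorder.

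**The C2 wording is only permissive, and may be meant as an exception to the exclusion before it.** Agreed, and the allowance may never have been used. Even so, its conditions are not given, and neither Table 1 nor C10 takes account of it.

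**The other safeguards cover everyone.** This stands in full. Protection is not absent; only the assurance of support after the visit is overstated.

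**Conclusion.** The plan's eligibility text contradicts the C10 statement on remission and does not secure it on residential care. The statement should be corrected because it is offered as a protection against a risk the plan itself identifies. The conclusion assumes that a current use disorder is not remission, and that C10 is not by itself operating as an unwritten screening rule.

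The size is unknown. The documents do not say how many subjects would be outside residential care or have current methamphetamine use disorder, and either number could be zero.

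Three stronger readings are tempting, and the documents support none of them.

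- **Unprotected subjects were enrolled.** The text shows only that a commitment is not carried into the criteria. It contains no enrolment data.
- **Half the sample is affected.** AUD and NAUD together make 2 × 50 = 100 of 200 planned subjects. That counts those the sentence describes, not those who lack the protection.
- **Treatment setting confounds the NAUD-versus-AUD relapse comparison in Hypothesis 2b.** That would need setting to vary and to differ between the two groups. Nothing in the documents shows either.

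**What to change.** 1. Reconcile the methamphetamine allowance with the rest of the eligibility text. Either withdraw it, or write it as an explicit exception in C2 and Table 1, with its conditions, and keep the record searches consistent with that choice.
2. Rewrite the C10 sentence so that it describes the subjects who are actually eligible.
3. For AUD, NAUD or methamphetamine subjects not in residential care, specify a contact shortly after the DSNBACK scan visit, with counseling referral. It can be by phone, as the between-visit calls in C1 already are, and the post-scan craving rating already collected can decide who is called first.

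The cost is protocol wording and a few extra calls. The phone screen already asks about treatment status, so staff need only note whether care is residential. Entering setting as a baseline data item is optional.

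Making residential care an entry requirement would also close the gap, but I would not advise it. C11 already describes recruitment as ambitious and depends on finding AUD subjects who do not use nicotine.
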